#### Control oximeter stability criteria

The control oximeter will provide the real time oxygen saturation level of the subject for determination of plateau levels and safety.

The data points are considered unstable and removed from the analysis:

- if the Control Oximeter SpO2 value varies by >2% during the draw time
- if the combined minimum and maximum deviations of the Control Oximeter SpO2 value are > 3% during the review period of 20-30 seconds prior to draw period through the draw as defined by ISO 80601-2.

#### **CO-Oximeter Data**

The CO-Oximeter data is reviewed for outliers or anomalous readings from which these plateaus are subject to removal. The functional oxygen saturation value will be used for the basis of comparison to  $SpO_2$  value collected from the pulse oximeter. Draws with COHb values >3% or MetHb values >2% or tHb <10 g/dl will be excluded from the data. When multiple CO-Oximeters are used, data that presents outliers from the other CO-Oximeters will be removed from the average of the CO-Oximeters. Outliers are defined as a CO-Oximeter  $SO_2$  values (functional oxygen saturation) that are >2% from the other CO-Oximeter's values. In the case where 2 CO-Oximeters are used, the data will be averaged unless the difference between the 2 CO-Oximeters is >2%. When the 2 CO-Oximeters deviate by >2%, the tHb, COHb, MetHb values will be reviewed for consistency to the other draws for this subject. If those values are found to be similar in readings for a given subject, then it is determined that the true reference value is unstable and the point will be removed from the analysis. If the finding is that one of the CO-Oximeter's has an  $SO_2$  value offset due to tHb, COHb or COHb values that are not similar for a given subject, then the offending CO-Oximeter will be rerun and if the offset persists, the value will not be used and the other CO-Oximeter  $SO_2$  value will be used as the reference for comparison.

Draws with CO-Oximeter data that are < 67% will be removed.

Test SpO2 Data will be removed for the following reasons:

- The test SpO2 values truncated at 100% or recorded >100% will be removed prior to the analysis.
- Zero values (drop outs in SpO2 or pulse rate) will be excluded from the calculations for the test SpO2.
- Perfusion level at the test site is determined to be too low for a valid reading.

A rationale will be provided for any data that is excluded from the data analysis.

Clinimark, LLC	TITLE: BORA Band SpO2 Validation Study	DOCUMENT NUMBER	REV
[name]	Study ID# PR 2018-312	PR# 2018-312	1
[name], USA	Principal Investigator: [name] Site ID # 001	Page 23 of 36	

The data will be plotted and analyzed through the following statistics, using the Reference CO-Oximetry SaO2 value for the x value and the Test Devices SpO2 value for the y value.

Ref = Reference CO-Oximetry SaO2 DUT = Device Under test SpO2

 $SpO_2$  accuracy will be evaluated for root-mean-square (rms) difference between the DUT and the reference for the specified  $SpO_2$  ranges (70-100%) and by  $SpO_2$  decade (90-100%, 80<90%, 70-<80%). The number of data points will be included for each statistic.

$$Arms = \sqrt{\frac{\sum_{i=1}^{n} (DUT_{i} - \text{Re } f_{i})^{2}}{n}}$$

The average difference is calculated to show the bias of the device under test as compared to the reference. The bias is calculated for the specified  $SpO_2$  ranges (70-100%) and by decade (90-100%, 80-<90%, 70-<80%).

$$Bias = \frac{\sum_{i=1}^{n} (DUT_{i} - \operatorname{Re} f_{i})}{n}$$

A least squares line (slope and intercept) will be generated for the overall range. The minimum and maximum deviations will be calculated from the reference.

Bland-Altman graphical plots, error ( $SpO_2 - SaO_2$ ) versus average  $SaO_2 + SpO_2$  will be generated with linear regression fit, mean, and upper 95% and lower 95% limits of agreement according to Section 3 of "Agreement Between Methods Of Measurement With Multiple Observations Per Individual" by Bland and Altman in 2007 Journal of Biopharmaceutical Statistics. Individual test subjects will be color coded in the Bland-Altman graphical plot.

Values for the population mean bias ( $\mu$ 0), between-subject variance ( $\sigma\mu$ 2) and within-subject variance ( $\sigma$ 2) will be calculated according to Section 3 of "Agreement Between Methods Of Measurement With Multiple Observations Per Individual" by Bland and Altman in 2007 Journal of Biopharmaceutical Statistics. Individual test subjects will be color coded in the Bland-Altman graphical plot.

Error plots (i.e., SaO2 versus (SpO2-SaO2) for both individual test subjects and all subjects pooled) will be generated.

Additionally, a scatter plot will be generated.

Test device outliers with a value >5% difference from the Reference CO-Oximeter will be discussed in the Final report per the FDA Guidance document for Pulse Oximeters.

Clinimark, LLC	TITLE: BORA Band SpO2 Validation Study	DOCUMENT NUMBER	REV
[name]	Study ID# PR 2018-312	PR# 2018-312	1
[name], USA	Principal Investigator: [name] Site ID # 001	Page 24 of 36	ᆂ

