# **Endpoint / Comparator**

The primary objective of this study is to validate SpO₂ accuracy performance of BiOSENCY BORA BAND™ wristband Pulse Oximeter by an Accuracy Root Mean Square (Arms) value. Reference CO-Oximetry will be used as the basis for comparison for the investigational device SpO₂ readings. The study population will include 10 to 15 subjects. The data for analysis will have approximately 200 data points equally distributed across the range of 70-100% by decade. All data will be used for the analysis unless a rational is provided for its removal. Possible reasons for data removal include, but are not limited to, unstable control, dashed or zero values, poor perfusion at the site, inconsistent or invalid CO-Oximetry values. Data that is found to not be useable will be removed prior to the comparative analysis. For the statistical analysis, the Accuracy Root Mean Square (ARMS) calculation is used to determine the SpO₂ accuracy performance providing documentation for the SpO₂ accuracy for the device under test during non-motion conditions.

There are no deviations expected from this investigation plan, should deviations be needed, discussions will be conducted with the sponsoring company and reported to the reviewing IRB per standard operating procedures.

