# Statistical Analysis

The purpose of this clinical study is to validate the SpO₂ accuracy of the BiOSENCY BORA BAND™ wristband Pulse Oximeter during non-motion conditions over the range of 70-100% SaO₂ as compared to arterial blood samples assessed by CO-Oximetry. Data analysis may occur in the following manner:

Data analysis will follow ISO80601-2-61:2017, Annex EE and the FDA Guidance Document for Pulse Oximeters (March 4, 2013). The reference guidance documents clearly define the study, number of subjects, data points needed for the analysis and handling of missing data or data that is removed from the analysis. This is achieved through a minimum of 200 paired observations of Test and Reference values equally distributed over the specified  $SpO_2$  accuracy range (70-100%) of the device under test.

Clinimark, LLC	TITLE: BORA Band SpO2 Validation Study	DOCUMENT NUMBER	REV
[name]	Study ID# PR 2018-312	PR# 2018-312	1
[name], USA	Principal Investigator: [name] Site ID # 001	Page 22 of 36	) <del>-</del>

The data will be collected on a minimum of 10 healthy adult volunteer subjects who range in age, gender and skin tone with 2 of the subjects or 15% of the subject pool (whichever is larger) having deep skin pigmentation tones. An Accuracy Root Mean Square ( $A_{RMS}$ ) calculation is used as a means to define the SpO2 Accuracy. The controls of the study will be provided in the following manner. The control oximeter will provide the real time oxygen saturation level of the subject for determination of plateau levels and safety. Additionally, the oxygen saturation values (SpO2) of a control oximeter will be used to assess the stability of the plateaus for data collection. There are no provisions for an interim analysis. For the validation, the SpO2 accuracy of test pulse oximetry system is compared to the Gold Standard measurement of blood SaO2 by a CO-Oximeter. Data analysis & demographics will be presented in the final report.

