# Pass / Fail Criteria

The statistical results of the data will be reviewed for the following pass/fail criteria:

SpO2 Accuracy for the range of 70-100%, ≤ 3.5 (ARMS) is a Pass for reflectance technology.

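### Test readings truncated at or recorded above 100% are removed on the device's own value; this can lower the pass/fail A_RMS, and no result that keeps them is planned

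*Combined protocol and SAP*

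**What the plan says.** The CO-Oximeter Data section lists reasons for removing test readings. The first is: "The test SpO 2 values truncated at 100% or recorded >100% will be removed prior to the analysis". The other two cover zero values (drop-outs) and readings at a site judged too poorly perfused. Range removal at the low end is set on the reference instead: "Draws with CO-Oximeter data that are < 67% will be removed".

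A_RMS and bias are then computed overall and by decade. Under Pass / Fail Criteria, an overall A_RMS of 3.5 or less over 70-100% "is a Pass for reflectance technology"; there is no other criterion.

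Several provisions bear on exclusions:
- Endpoint / Comparator: "All data will be used for the analysis unless a rational is provided for its removal".
- CO-Oximeter Data: "A rationale will be provided for any data that is excluded from the data analysis". With the formulas: "The number of data points will be included for each statistic", and "Test device outliers with a value >5% difference from the Reference CO-Oximeter will be discussed in the Final report".
- Statistical Analysis says that the cited ISO standard and FDA guidance define, among other things, the "handling of missing data or data that is removed from the analysis".
- Criteria for Study Termination asks for justification of data excluded from terminated sessions.
- Data and Quality Management / Confidentiality preserves the original device files.

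The device description lists a ratio of ratios and/or an SpO2 value among the collected data. It does not say whether SpO2 is clipped at 100.

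**The concern.** The rule selects pairs on the measurement being validated. At SaO2 97, a reading of 103 (error +6) is deleted, but a reading of 91 (error -6) stays and counts. Zero drop-outs and low-perfusion readings are also removed on the test side, but as invalid readings. A low, non-zero, valid reading has no matching removal.

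The rule also treats two different things alike. A value recorded above 100% has a known positive error. A value truncated at 100% has a censored error: its true size is hidden.

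The only pass criterion is a pooled A_RMS computed after this removal. The Procedure section plans sampling at 95-100 and 90-95, so the rule can act on data the design sets out to collect. Without a second result, a reader cannot see whether a pass rests on it.

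**Working it through.** **The plan's own count.** Ten subjects at 20 points each give 10 x 20 = 200, the stated minimum number of pairs. The documents give no power calculation, bias or SD, so the rest uses stated assumptions.

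**Check 1: arithmetic with no error model.** Suppose 200 retained pairs have A_RMS A, and m removed pairs have rms error e. Keeping them gives sqrt((200A² + m·e²)/(200 + m)).
- A = 3.40, m = 20, e = 5: sqrt((2312 + 500)/220) = 3.58. A pass becomes a fail.
- A = 3.40, m = 10, e = 6: sqrt((2312 + 360)/210) = 3.57. A pass becomes a fail.
- A = 3.55, m = 20, e = 2: sqrt((2520.5 + 80)/220) = 3.44. Here a fail becomes a pass, so removal can also count against the device.

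For A = 3.40, keeping the pairs pushes A_RMS over 3.5 when e exceeds 5.1 (m = 10) or 4.4 (m = 20).

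**Check 2: error model.** From the Procedure section: six levels (95-100, 90-95, 85-90, 80-85, 75-80, 67-75). Assumed: equal weight per level, SaO2 uniform within each, error normal with bias b and SD s. A second run takes the top level as 94-98. Readings of 100 or more count as removed.

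Let c = 100 - SaO2 and z = (c - b)/s:
- fraction kept: Φ(z)
- sum of squares kept: (b² + s²)Φ(z) - s(b + c)φ(z)
- readings kept at a cap of 100 add (1 - Φ(z))c²

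Averaging over levels and taking roots gives the pooled A_RMS (top level 95-100, with 94-98 in brackets):

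| Assumed error | Uncapped, kept | Removed | Capped, kept at 100 |
|---|---|---|---|
| b = +2, s = 3.0 | 3.61 | 3.42 [3.41] | 3.39 [3.46] |
| b = 0, s = 3.7 | 3.70 | 3.60 [3.59] | 3.58 [3.61] |
| b = -2, s = 3.0 | 3.61 | 3.61 [3.60] | 3.59 [3.60] |
| b = +1, s = 2.0 | 2.24 | 2.17 [2.18] | 2.16 [2.21] |
| b = +4 at SaO2 ≥90, 0 below; s = 3.0 | 3.79 | 3.17 [3.18] | 3.24 [3.37] |

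The uncapped column is simply sqrt(b² + s²), for example sqrt(4 + 9) = 3.61. The last row is sqrt((2 x 25 + 4 x 9)/6) = 3.79. The first three rows were chosen to lie near 3.5, and the last is a constructed case.

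**Probability of a pass.** From 20,000 simulated studies of 10 subjects x 24 points, at intraclass correlation 0.2 / 0.4, top level 95-100:
- b = +2, s = 3.0: uncapped 0.40 / 0.45; removed 0.64 / 0.62; capped 0.69 / 0.65.
- +4 case: uncapped 0.11 / 0.20; removed 0.97 / 0.91; capped 0.94 / 0.87. With top level 94-98, capped is 0.80 / 0.75.
- b = +1, s = 2.0: 1.00 throughout.

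**The 90-100% decade.** At b = +2, s = 3.0, removal deletes 24% [16%] of its points. Its A_RMS falls from 3.61 to 2.89 [2.91] and its bias from +2.0 to +1.1 [+1.3]. Of 80 points there, about 80 x 0.159 = 12.7 have errors above +5. About 8 of these are deleted, and none below -5. The downward shift need not flatter the device: at b = 0, s = 3.7, decade bias becomes -0.8 [-0.6].

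**Check 3: a different layout.** Here SaO2 was spread equally by decade, with a maximum of 98, 99 or 100, and removal applied when the rounded reading was 100 or more. Against uncapped values, removal lowered A_RMS in all 27 scenarios: by 0.06 to 0.22 in 24 with uniform bias, and by 0.38 to 1.18 in three with over-reading concentrated at 90-100. Against capped values, uniform-bias gaps ran from about 0.06 lower to 0.07 higher; the largest concentrated case was 0.40 lower.

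**The case against.** The strongest reply is that the large effects need exported values above 100%. The removal rule provides for such values, but nothing in the documents confirms that they occur. That stands. For capped output, the sign of the difference turns on how close SaO2 comes to 100: with the top level at 95-100, removal is slightly stricter than keeping at 100 in all four uniform-bias rows. Keeping a censored reading at 100 is therefore not a cleaner benchmark.

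Nor does any figure in the documents place this device near 3.5, and the +4 pattern has no source there. That also stands; the table shows what the rule can do and predicts nothing about this device.

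The rule is pre-specified, exclusions need a rationale, n is reported and original files are kept. This guards against after-the-fact choice and makes re-analysis possible, but no such re-analysis is planned. A reader might infer that deleted readings escape the >5% discussion. The text does not say so: removal comes first, but the discussion is not expressly limited to retained pairs.

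Finally, the plan defers the handling of removed data to outside guidance. If that guidance requires this removal, changing the pass/fail data set would conflict with it. It cannot be checked here, so that part of the fix must be conditional.

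**Conclusion.** The concern holds as a possibility, not a prediction. If values above 100% are exported, removal can lower the deciding A_RMS: by 0.18 at bias +2 and SD 3.0 (3.606 to 3.422), enough to cross the limit, and essentially not at all at bias -2. For capped output in the main model, the gap between removing and keeping at 100 is about 0.05 or less for uniform bias, in either direction. It is 0.07 to 0.19 lower in the constructed +4 case. All sizes rest on assumed bias, SD, normal errors and SaO2 spread, so no bound is claimed.

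A reader might infer that the rule always favours the device, or that it breaches the cited guidance. The documents support neither: the capped cases and the third line of Check 1 go the other way, and the guidance is not available here. What they do show is that no planned result would reveal whether a pass depends on the rule.

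**What to change.** Amend the CO-Oximeter Data section and the analysis text that follows it, before analysis:

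1. Treat values recorded above 100% separately from values truncated at 100%.
2. Keep recorded values above 100% in the pass/fail A_RMS, unless the guidance cited under Statistical Analysis requires their removal. In that case cite the requirement, and report A_RMS and bias with them kept as a pre-specified sensitivity result.
3. For values truncated at 100%, keep the current rule for pass/fail. Also report overall and 90-100% A_RMS and bias with them kept at 100.
4. Report the number removed per decade and per subject with paired SaO2, and include these pairs in the >5% outlier discussion. Say in the conclusion if pass/fail differs between results.

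The cost is plan wording and one or two extra result lines; the preserved original files supply the data. A_RMS may become less favourable if values above 100% are kept.

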# **Objectives of the Clinical Investigation Plan**

The purpose of this clinical study is to validate the SpO2 accuracy of the BiOSENCY BORA BAND™ wristband Pulse Oximeter during non-motion conditions over the range of 70-100% SaO2 as compared to arterial blood samples assessed by CO-Oximetry. The end goal is to provide supporting documentation for the SpO2 accuracy validation of BORA BAND™ wristband Pulse Oximeter.

It is required that the Accuracy Root Mean Square (ARMS) performance of the BORA BAND™ wristband Pulse Oximeter will meet a specification of 3.5 or better in non-motion conditions for the range of 70 − 100% SpO2 thereby demonstrating an acceptable SpO2 accuracy performance specification.

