# BORA Band SpO2 Validation Study PR 2018-312

# **Objectives of the Clinical Investigation Plan**

The purpose of this clinical study is to validate the SpO2 accuracy of the BiOSENCY BORA BAND™ wristband Pulse Oximeter during non-motion conditions over the range of 70-100% SaO2 as compared to arterial blood samples assessed by CO-Oximetry. The end goal is to provide supporting documentation for the SpO2 accuracy validation of the BiOSENCY BORA BAND™ pulse oximetry.

It is required that the Accuracy Root Mean Square (ARMS) performance of the BiOSENCY BORA BAND™ pulse oximetry will meet a specification of 3.5 or better in non-motion conditions for the range of 70 − 100% SaO2 thereby demonstrating an acceptable SpO2 accuracy performance specification.

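### A_RMS decades are worded on SpO2 and start at 70%, although draws are kept from 67% SaO2; no rule says which variable assigns a point to a decade

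*Combined protocol and SAP*

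**What the plan says.** **Set that is collected and kept**
- *Summary Overview (Synopsis)*: at least 200 points from at least 10 subjects over 70-100% SaO2, with an allowance of 3% around the range.
- *Procedure, step 28*: six plateau ranges, the lowest being 67-75.
- *CO-Oximeter Data*: draws with a CO-Oximeter value below 67% are removed. Test readings are removed if truncated at or above 100%, if zero, or if perfusion is too low. Reference SaO2 is the x value and test SpO2 the y value.

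**How the statistics are worded** (text following *CO-Oximeter Data*)
- The test reading is given as "DUT = Device Under test SpO 2".
- A_RMS is evaluated for the specified SpO2 range of 70-100% and by SpO2 "decade (90-100%, 80<90%, 70-<80%). The number of data points will be included for each statistic".
- Bias is calculated for the specified SpO2 "ranges (70-100%) and by decade (90-100%, 80-<90%, 70-<80". This sentence names no variable for its decades.
- The plots include "Error plots (i.e., SaO 2 versus (SpO 2 -SaO 2").

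**Criterion and objective**
- *Pass / Fail Criteria*: A_RMS of 3.5 or less for 70-100% "is a Pass for reflectance technology". Neither the range variable nor the 3% allowance is stated.
- *Objectives (Synopsis)*: the opening sentence is "over the range of 70-100% SaO 2 as compared to arterial blood samples assessed by CO-Oximetry", but the 3.5 specification is "for the range of 70 − 100% SpO 2".
- *Objectives (body)*: the same specification is "for the range of 70 − 100% SaO 2".

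**The concern.** A stratified accuracy table needs a stated rule for placing each pair in a stratum. Here the only decade rule that names a variable names SpO2, and the lowest stratum begins 3 points above the floor down to which data are deliberately collected and kept.

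Either way of applying the rule causes a problem. If the test reading assigns the decade, pairs are sorted partly on their own error. Pairs that read low fall into lower decades and pairs that read high into higher ones, so an unbiased device shows bias in its decade results. If reference SaO2 assigns the decade, the 67-<70% draws belong to no listed stratum, and the decade counts do not add up to the overall count.

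The same 67 v 70 mismatch runs into the single pass/fail criterion, whose range is given as 70-100% without the allowance. The lowest saturations are where a device's error may be largest, so whether those draws count should be stated before the data are seen.

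**Working it through.** **1. The plan's own figures.** The floor is 70 - 3 = 67, which matches the 67% removal rule and the 67-75 plateau. The minimum is 10 subjects x 20 points = 200, which matches the stated 200. The documents give no SD, bias, alpha or power, so every error model below is an assumption.

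**2. How many draws lie at 67-<70%.** Assume the six plateau ranges of step 28 are filled equally and SaO2 is uniform within each.

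Share = (70 - 67)/(75 - 67) x 1/6 = 3/8 x 1/6 = 0.0625.

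With 10 subjects x 4 draws x 6 ranges = 240 draws, 0.0625 x 240 = 15. About 230 of the 240 remain once test readings at or above 100 are removed. The listed decades, assigned by SaO2, would then hold about 230 - 15 = 215. For 200 points the count is 0.0625 x 200 = 12.5. If SaO2 were instead uniform over 67-100, it would be 200 x 3/33 = 18.2. A 200-point set without this band would hold about 182 to 188, below the plan's minimum.

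**3. Effect of the decade variable.** Model: SpO2 = SaO2 + bias x (100 - SaO2)/30 + normal error, readings at or above 100 removed, 4 million points per scenario. For an unbiased device with SD 3.45:

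| Decade | Mean error, binned on SpO2 | Mean error, binned on SaO2 |
|---|---|---|
| 70-<80% | -0.66 | 0.0 |
| 90-100% | +0.68 | -0.69 |

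The lowest-decade figure under SpO2 binning is purely an effect of sorting. The top decade is distorted under either rule, because removing readings at or above 100 takes out high readings. If binned on SpO2, about 34% of the 67-<70% draws would enter the 70-<80% decade.

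**4. Effect of a 67% v a 70% SaO2 cut on the overall A_RMS.** With SD 3.3 and bias falling to -3 at 70% saturation, A_RMS is 3.71 to 3.72 across repeat runs with the 67% floor and 3.65 with a 70% cut, a difference of 0.06 to 0.07. For the unbiased device with SD 3.45 it is 3.37 v 3.36, a difference of 0.01. Over all the models the difference is 0.00-0.07.

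The next table gives the share of simulated trials (10,000 per scenario, 240 draws each) in which the verdict at 3.5 depends on the cut:

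| Assumed device | No error variance between subjects | 50% between subjects |
|---|---|---|
| SD 3.3, bias to -3 | about 11% | about 6% |
| SD 3.3, bias to -2 | about 10% | about 4% |
| SD 3.3, bias to +3 | about 13% | about 7% |
| SD 3.45, unbiased | about 5% | about 3% |
| SD 2.4, unbiased | 0% | 0% |

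For the biased devices nearly all changes run from fail with the 67% floor to pass with a 70% cut. For the unbiased SD 3.45 device they run about equally both ways.

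**5. Effect on the lowest-decade A_RMS.** Reporting 67-<80% instead of 70-<80% gives 4.20 v 4.11 with bias to -3, and 3.45 v 3.45 for the unbiased SD 3.45 device.

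**The case against.** The strongest reply is that the overall pass/fail set can already be inferred. The Synopsis states the 3% allowance on SaO2. *Endpoint / Comparator* uses all data unless a reason for removal is given. *CO-Oximeter Data* sets the floor at 67%, and its list of reasons for removing test data includes neither a reading below 70 nor an SaO2 of 67-<70%. A cut at 70% would be an unlisted exclusion needing a rationale, or a deviation to be justified in the final report. The list in *Endpoint / Comparator* is expressly not exhaustive, so this is strong inference and not an explicit rule, but it largely stands.

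It also stands that the plan does not reserve the bare term SpO2 for the test device. *Criteria for Study Termination* uses it for target levels, and *Control oximeter stability criteria* uses it for the control oximeter. *Statistical Analysis* speaks of the specified SpO2 accuracy range of the device under test, meaning its claimed range, and the range wording in the A_RMS and bias sentences probably repeats that. This does not explain an instruction to report by SpO2 decade, nor does it supply a stratum below 70%.

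It is true, too, that decade results carry no pass/fail rule, that counts are reported with each statistic so a gap would be visible, and that the error plots against SaO2 would show the draws. Visibility afterwards is weaker than a rule fixed beforehand, but it limits the harm. The plan also refers to an ISO annex and FDA guidance for the handling of removed data. Those are not available here, and whether they settle the binning cannot be judged.

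**Conclusion.** The wording conflict is real and minor. The decade rule is unsound as written. It either sorts pairs on the device's own error or leaves about 15 of 230 retained draws without a decade, given equal and uniform filling of the plateaus. The 67 v 70 mismatch in the pass/fail wording is worth 0.00-0.07 in A_RMS, and changes the verdict in about 3-13% of trials for an assumed device near 3.5. It changes none for an unbiased device with SD 2.4.

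A reader might go further and infer that the pass/fail A_RMS is to be computed only on pairs whose test SpO2 is 70-100%, which would discard the low readings of an under-reading device. In the model with bias to -3 that would bring A_RMS down to 3.36. The documents do not support this reading: no removal rule targets low test readings, reference SaO2 is the x variable, and the SpO2 range most likely names the claimed range. The size of the problem should not rest on it. Nor do the documents support saying that the pass/fail set is undefined, since SaO2 of 67% or more is strongly implied.

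**What to change.** In the A_RMS and bias definitions and in *Pass / Fail Criteria*, state once that:
- reference SaO2 assigns each pair to the range and to a decade;
- the pass/fail A_RMS uses all usable draws with SaO2 67-100%, as the Synopsis allowance and the 67% removal rule imply;
- the lowest decade is 67-<80%, and is labelled so.

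Align the specification sentence in the Synopsis Objectives with the SaO2 wording in the body.

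This is a change of wording only, with no extra draws or subjects. The downside is that A_RMS may come out slightly less favourable than with a 70% cut, by up to 0.07 in the assumed models. Assigning decades by SaO2 removes the artefact in the lowest decade only. The top decade remains affected by the removal of readings at or above 100, and the report should say so beside that result.
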